3.1 Benefits

There will be considerable benefits to the participants enrolled in the proposed study. All participants will receive information about how to reduce cardiovascular disease risk, and how to increase physical activity or improve your diet. In addition, participants in the active treatment group will receive free health coaching, while participants in the attention control group will have a trained research assistant deliver health related education.

3.2 Risks

Potential risks of research participation-physical, psychological, financial and legal risks among others-are considered minimal. In-home evaluations and assessments of barriers may result in fatigue or aggravation. In addition, some questions may touch on emotionally-sensitive issues that could cause anxiety or other forms of emotional stress. The performance-based testing involves observation of everyday activities, which may result in fatigue or embarrassment.

Participants will be told that their involvement in this research study is voluntary and that they may choose not to participate or withdraw their consent at any time. Withdrawal from the study will not at any time affect the commitment of the clinician to administer care, and there will be no penalty or loss of benefits to which participants are otherwise entitled. Participants who undergo the study visits will be given the option to reschedule the visit or take a break at any time during the study if necessary. There is little legal risk to participating in this research. All research-related information will be kept confidential and accessible only to authorized members of the research team.

3.3 Minimization of Risks

We are a HIPPA covered entity and comply with all HIPPA regulations. To protect against and minimize potential risks, participants will be carefully screened and evaluated for eligibility by research coordinator.

To avoid or minimize symptoms of fatigue, agitation, or emotional distress due to testing, participants will be instructed to notify the rater or interventionist if they experience any discomfort. They will also be periodically questioned about their tolerance for the tests/intervention. Testing and interviews will be terminated if participants develop fatigue, agitation, or emotional distress.

An ID number will be assigned to each participant. All data collected from a participant will be labeled with the ID number. All participant electronic and hard-copy data will be kept under double-lock protection. All hard copy forms that contain personal identifiers (e.g., name, address, phone numbers) will be stored in a separate locked file drawer under double-lock protection. No publication or presentation of the study data will uniquely identify or provide sufficient information to uniquely identify participants.

Risks during the home visit will be minimized by having licensed and trained interventionists available to monitor safety during intervention.

To guard against unauthorized data access, all shared-use computer systems at the lab are protected with passwords, which are changed at 4-month intervals. Only individuals with a particular "need to know" status are given access, and system privileges are carefully restricted. All personal computers to be used in the Administrative Unit are located within a secure area, and the system is locked when not in use. SPSS software packages will be used for data management and analysis. Datasets generated from these programs will not contain any HIPPA data.

Data will be entered into a REDCap database. REDCap servers are securely housed in an onsite, limited-access data center managed by the Wayne State University IT. All data are stored on a private, firewall protected network. All users are given individual user IDs and passwords, and their access is restricted on a role-specific basis. REDCap was developed specifically around Health Insurance Portability and Accountability Act security guidelines and is implemented and maintained according to Washington University guidelines. Study data will be collected via tablet in the field and managed using REDCap electronic data-capture tools hosted at Washington University. REDCap is a secure, Web-based application designed to support data capture for research studies.

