1.3.7 Intervention period

The treatment group will receive habit formation intervention for 12 weeks. The HF intervention is delivered by an experienced geriatric occupational therapist. The 12-week long, intervention is delivered to each participant during 12 face-to-face, home based sessions (each lasting ~60 minutes). An initial session (week 2) focuses on welcoming the participant to the program, and delivering educational content about prefrailty, frailty protective behaviors, and the concept of HF. In preparation for the sessions covering ST reduction and MVPA the next session (week 3) focuses on pain, its management, and the relationship between pain and activity (described below). Weeks 3-11 include weekly HF sessions focused on ST reduction, MVPA and dietary behaviors (see Table 2 for session content). A closing session occurs in week 12 to review program progress and create maintenance plans.

The control group will receive 12 weeks of newsletters focused on general healthy aging topics. Within 4 days of mailing the newsletter, the coordinator will call the participant, verify receipt of the newsletter, and ask them if they have any questions about the materials. Phone

call will last ~15 minutes. Control condition participants receive no further intervention.

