3.4 Adverse events

- What is an adverse event?

An adverse event is any reaction, side effect or untoward event that occurs during the course of the study. Adverse events are categorized as serious (see below) or non-serious, as related or not related to the study intervention, and as expected or unexpected. For the purpose of the present trial, clinically insignificant events will be excluded from any type of AE documentation. These include colds, flu, cuts, scrapes, coughs, headaches, stomach complaints, general fatigue and mild symptoms. Behavioral AEs that will be tracked in this trial include increases in emotional distress and problems managing everyday activities (functional changes).

Serious adverse events (SAEs) are defined as deaths, life-threatening events, permanently or substantially disabling events, congenital anomalies, events requiring an initial hospitalization or prolonging a current hospitalization, or events that require intervention to prevent permanent impairment or damage. SAEs in this trial could include inpatient hospitalization for cardiovascular or other cardio-metabolic disease related problems.

- In the visit, if there is an SAE that is emergent, call 911.
- Document AE in rater's log in Redcap.
- Notify Study coordinator immediately if there is an AE or SAE.

4. References

1. Fried, L. P., Tangen, C. M., Walston, J., Newman, A. B., Hirsch, C., Gottdiener, J., ... & McBurnie, M. A. (2001). Frailty in older adults evidence for a phenotype. *The Journals of Gerontology Series A: Biological Sciences and Medical Sciences*, 56(3), M146-M157.
5. Gill, T. M., Gahbauer, E. A., Allore, H. G., & Han, L. (2006). Transitions between frailty states among community-living older persons. *Archives of internal medicine*, 166(4), 418-423.

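### No adverse-event question common to both arms is specified, so any adverse-event count reported by arm would be open to ascertainment bias

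*Combined protocol and SAP*

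**What the plan says.** Section 3.4 counts anything untoward that happens while the study is running as an AE, apart from a list of minor complaints. It singles out worsening emotional distress and loss of everyday function for tracking. Its instructions are written for raters at visits, for example "In the visit, if there is an SAE that is emergent, call 911". AEs go into the rater's log in REDCap, and the study coordinator is to be told at once. The section gives no AE question, schedule or recall period.

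Section 1.3.7 sets the contacts during the intervention. The treatment arm has 12 face-to-face home sessions of about an hour with an occupational therapist. For controls, "The control group will receive 12 weeks of newsletters focused on general healthy aging topics". After a mailing, "the coordinator will call the participant, verify receipt of the newsletter, and ask them if they have any questions about the materials", and the "call will last ~15 minutes". Nothing further is provided for controls, and the number of calls is not stated.

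Section 3.3 adds "Risks during the home visit will be minimized by having licensed and trained interventionists available to monitor safety during intervention". It also tells participants, without naming an arm, to report discomfort to the rater or interventionist, and says "They will also be periodically questioned about their tolerance for the tests/intervention". The aim given there is to limit fatigue, agitation or distress caused by testing.

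Table 1 in section 1.3.8 places rater assessments at baseline (weeks 1-2) and week 15 and lists no AE form at either. Section 2.1 plans no AE analysis.

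**The concern.** How many events are recorded depends on how many occur and on how hard anyone looks. Here the looking differs by arm in mode, staff, length and content. A treatment participant is seen repeatedly at home by a clinician charged with monitoring safety. A control speaks by telephone to a coordinator whose listed topics do not include health. Of the two people to whom participants are told to report discomfort, controls have no interventionist, and no rater assessment is scheduled between baseline and week 15.

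Two things are at stake. If AEs are tabulated by arm, as readers of a randomized trial will expect, a difference could reflect closer observation rather than harm, and a real excess could be explained away in the same manner. Judging whether an event is related to the intervention, which section 3.4 requires, also lacks a fair control background. Separately, an event in a control may come to light late.

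**Working it through.** **Figure to reproduce.** There is none. The documents give no AE rate, no detection rate and no safety sample size, and section 2.2 says that no power analysis was done.

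**Contacts side by side, between baseline and week 15.**

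| | Treatment | Control |
|---|---|---|
| Mode (1.3.7) | Face to face, at home | Telephone |
| Staff (1.3.7) | Occupational therapist | Coordinator |
| Number (1.3.7) | 12 | Not stated |
| Length (1.3.7) | About 60 min | About 15 min |
| Safety role (3.3) | Interventionist monitors safety | None stated |
| Scripted AE question | None | None |
| Rater assessment (Table 1) | None | None |

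**Scheduled contact time.** Minutes = contacts × minutes per contact.

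- Treatment: 12 × 60 = 720.
- Control, assuming one call per week: 12 × 15 = 180; 720 / 180 = 4, a ratio of 4:1.
- Control, assuming 6 calls: 6 × 15 = 90; ratio 8:1.
- Control, assuming 3 calls: 3 × 15 = 45; ratio 16:1.

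So 4:1 is the smallest imbalance over the assumed range of 3 to 12 calls. Contact time shows that opportunity is unequal; it does not measure detection.

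**Illustration of the effect on counts.** Let n be participants per arm, p the true proportion with a reportable event (equal in both arms), and d the proportion of those detected. Expected number recorded = n × p × d. With 1:1 allocation (section 1.3.5) and equal p, the apparent ratio is d(treatment) / d(control), whatever n and p are. All values of d below are assumptions.

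- 0.90 / 0.90 = 1.0
- 0.90 / 0.80 = 1.125, about 1.1
- 0.90 / 0.70 = 1.29
- 0.90 / 0.60 = 1.5
- 0.90 / 0.50 = 1.8

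For absolute numbers, assume p = 0.20 with d = 0.90 and 0.50. Section 2.2 gives 15 per group, and section 1.3 gives 80 in total, which is 40 per arm at 1:1. The documents do not reconcile these, so both are shown.

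- n = 15: 15 × 0.20 × 0.90 = 2.7 against 15 × 0.20 × 0.50 = 1.5.
- n = 40: 40 × 0.20 × 0.90 = 7.2 against 40 × 0.20 × 0.50 = 4.0.

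At 15 per arm the gap is about one participant, so a single missed event can change the picture.

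**The case against.** Several stronger readings are tempting, and the documents do not support them.

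- *Only treatment participants are questioned about tolerance.* The sentence in section 3.3 names no arm, covers tests as well as intervention, and mainly concerns discomfort from testing. What can be said is that between baseline and week 15 only the treatment arm has scheduled in-person contact at which such questioning could happen.
- *Harms can surface only through arm-specific contacts.* Controls can volunteer an event on a call or at week 15, and the caller is a coordinator, the role that section 3.4 says must be notified.
- *AE counts by arm are biased, so the pilot fails on safety.* Section 2.1 plans no such comparison and the hypotheses in section 1.1 set no safety aim. This is a risk of bias if counts are reported by arm, not a bias shown to exist.
- *Serious control events go unnoticed for about 13 weeks.* That is the whole interval (week 15 minus week 2) and assumes that no call reveals anything. Hospital stays and deaths depend less on contact intensity than milder or behavioral events do.

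The direction is also less certain than it looks. No AE question is written for treatment sessions either, and section 3.4 names only the rater's log, so an event heard by the therapist has no stated recording route beyond telling the coordinator. Section 3.1 describes a research assistant delivering education to an attention control group, which does not match section 1.3.7 and leaves actual control contact unclear. The Geriatric Depression Scale, WHOQOL-BREF and SPPB are scheduled at baseline and week 15 without restriction to one arm and partly cover distress and function, but none is designated as an AE source and none would record an injury or a hospital stay.

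These points limit the claim. They do not supply a common means of asking about events.

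**Conclusion.** The point holds in a limited form. AEs are to be tracked throughout, scheduled contacts between baseline and week 15 differ by arm, and no AE question common to both arms is specified at any time, including week 15. Any AE count reported by arm would be open to ascertainment bias. The likely direction is more recorded events under treatment, mainly non-serious and behavioral ones; this is an inference from the contact pattern, not something the text establishes. Control events may also be recognised late.

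The size cannot be computed from the documents. The apparent ratio of 1.8 to 1.1 rests wholly on assumed detection of 90% against 50-80%, and the 4:1 contact ratio on assumed weekly calls. The change is worth making because it is cheap and because events not asked about at the time cannot be recovered reliably later.

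**What to change.** 1. In sections 1.3.7 and 3.4, add the same short scripted question to treatment sessions and control calls, on the same schedule: any fall, injury, new or worse health problem, emergency visit or hospital stay since the last contact, and any increase in distress or difficulty with daily activities. State the number of control calls so that the schedules can match, and reconcile sections 1.3.7 and 3.1 on what controls receive.
2. State that the therapist and the coordinator log these answers in REDCap, in a form the blinded raters cannot see. Section 1.3.5 says the coordinator who randomizes takes no part in data collection; if the same person calls controls, that wording needs a matching change.
3. At week 15, the rater asks both arms the same question about the period since baseline, after the outcome measures and with an instruction to participants not to disclose their arm. Add this to Table 1.
4. In section 2.1, plan to report the number of participants with at least one event per arm, by source of detection. Include events known for participants who died or withdrew before week 15, and do not rely on the week 15 question alone, since it misses them.

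**Cost.** About 1-2 minutes per contact and a small REDCap form. More control events will need recording, recall at week 15 will be imperfect, and there is a small risk of unblinding raters, which asking last reduces but does not remove.

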3.4 Adverse events

- What is an adverse event?

An adverse event is any reaction, side effect or untoward event that occurs during the course of the study. Adverse events are categorized as serious (see below) or non-serious, as related or not related to the study intervention, and as expected or unexpected. For the purpose of the present trial, clinically insignificant events will be excluded from any type of AE documentation. These include colds, flu, cuts, scrapes, coughs, headaches, stomach complaints, general fatigue and mild symptoms. Behavioral AEs that will be tracked in this trial include increases in emotional distress and problems managing everyday activities (functional changes).

Serious adverse events (SAEs) are defined as deaths, life-threatening events, permanently or substantially disabling events, congenital anomalies, events requiring an initial hospitalization or prolonging a current hospitalization, or events that require intervention to prevent permanent impairment or damage. SAEs in this trial could include inpatient hospitalization for cardiovascular or other cardio-metabolic disease related problems.

- In the visit, if there is an SAE that is emergent, call 911.
- Document AE in rater's log in Redcap.
- Notify Study coordinator immediately if there is an AE or SAE.

4. References

1. Fried, L. P., Tangen, C. M., Walston, J., Newman, A. B., Hirsch, C., Gottdiener, J., ... & McBurnie, M. A. (2001). Frailty in older adults evidence for a phenotype. *The Journals of Gerontology Series A: Biological Sciences and Medical Sciences*, 56(3), M146-M157.
5. Gill, T. M., Gahbauer, E. A., Allore, H. G., & Han, L. (2006). Transitions between frailty states among community-living older persons. *Archives of internal medicine*, 166(4), 418-423.

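### Section 3.4 keeps mild events out of the adverse-event record, and the supplied text lists no scheduled, recorded question on falls, injury or activity-related pain in either arm

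*Combined protocol and SAP*

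**What the plan says.** Section 3.4 defines an adverse event broadly and then narrows what is written down: "For the purpose of the present trial, clinically insignificant events will be excluded from any type of AE documentation". The examples follow: "These include colds, flu, cuts, scrapes, coughs, headaches, stomach complaints, general fatigue and mild symptoms". No severity threshold, relatedness test or decision-maker is given for the last category. The behavioural events singled out for tracking are greater emotional distress and difficulty with daily activities. Serious events follow a conventional definition that includes hospitalization. The recording instructions are "Document AE in rater's log in Redcap" and "Notify Study coordinator immediately if there is an AE or SAE".

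Section 3.2 names fatigue as a risk of the study visits: "In-home evaluations and assessments of barriers may result in fatigue or aggravation". Neither 3.2 nor 3.4 names falls, musculoskeletal injury or activity-related pain.

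Section 3.3 adds safeguards. It says "participants will be instructed to notify the rater or interventionist if they experience any discomfort", and then "They will also be periodically questioned about their tolerance for the tests/intervention". It gives no interval, form or place of recording for those questions. It also says that trained interventionists monitor safety during the intervention.

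Pain appears in two other places. A typical daily rating of 7/10 or more is an exclusion criterion (1.3.1), screened by phone (1.3.2), and one early treatment session covers pain and activity (1.3.7). Neither is a repeated, recorded measure.

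**The concern.** More standing, walking and moderate-to-vigorous activity in prefrail people can plausibly bring minor falls, strains and soreness. These are the events a pilot is well placed to count before a larger trial. Under 3.4 a minor fall with a scrape, or soreness after added activity, may be judged clinically insignificant and left out. Where no one is asked on a schedule, a low count could mean few events or few questions, and the plan gives no way to tell which.

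The arms also differ in their opportunity to mention an event. Treatment participants see a therapist at home; controls receive short calls about the newsletter. Counts that depend on unprompted mention would not be comparable by arm. The feasibility outcomes named in 2.1 (recruitment, retention and attendance) would reveal poor tolerability only in part.

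**Working it through.** The documents give no figure on this point to reproduce. The check compares the sections and adds some simple arithmetic.

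1. **What is excluded (3.4).** The list has 9 categories: colds, flu, cuts, scrapes, coughs, headaches, stomach complaints, general fatigue, mild symptoms. Four of them (cuts, scrapes, general fatigue, mild symptoms) could readily follow a minor fall or added activity. This sorting is a judgement; a headache could also follow a fall.

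2. **Fatigue across sections.** It is a stated risk in 3.2 and a reason to stop testing in 3.3, yet general fatigue is kept out of the event record in 3.4.

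3. **What is scheduled (Table 1 and 2.3).** Of the 15 numbered items in Table 1, 0 are listed as a falls, injury, pain or adverse-event question. The exhaustion component of the frailty criteria touches fatigue at two time points, but not falls, injury or pain.

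4. **Opportunity to report (1.3.7).** Treatment: 12 sessions × about 60 min = 720 min. Control: 12 calls × about 15 min = 180 min, if there is one call a week. The text says only that newsletters run for 12 weeks, so the weekly call is an assumption. On it, contact time differs by 720/180 = 4 times.

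5. **What asking everyone would allow.** Section 2.2 gives 15 per group, and 1.3 gives 80 in total, or 80/2 = 40 per arm, so both sizes are shown. With zero events among n people who were all asked, the one-sided 95% upper bound on risk is 1 − 0.05^(1/n):
   - n = 15: 1 − 0.05^(1/15) = 0.181, or 18.1%
   - n = 40: 1 − 0.05^(1/40) = 0.072, or 7.2%

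6. **What a repeated pain rating would give.** The 95% half-width of a mean change within one arm, in units of the SD of the change scores, is t(n−1)/√n:
   - n = 15: 2.145/√15 = 0.55 SD
   - n = 40: 2.023/√40 = 0.32 SD

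Steps 5 and 6 describe what the change would buy. They do not measure harm done by the present plan, and at 15 per arm they show that the added information would be coarse.

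**The case against.** The plan is not silent on safety. Its event definition is broad, any hospitalization is a serious event, the coordinator is told at once, participants are asked to report discomfort, and tolerance is checked periodically. This is a behavioural pilot that the protocol regards as minimal risk, and leaving colds and coughs out of the log is reasonable. Grip strength, walking, the SPPB, depressive symptoms and quality of life are measured in both arms at w1 and w15, and data collectors are blinded (1.3.5). All of this stands, and it limits the point to minor or transient events and to comparability by arm. It does not remove the point: the tolerance question has no stated interval or record, and a mild answer would still meet the exclusion.

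Three stronger readings are tempting, and the documents do not support them:

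- **That falls and injuries may not be recorded at all.** They are not on the excluded list. Anything more than mild, or anything that limits daily function, fits the definition and can be logged if reported.
- **That therapists and control callers have no way to record an event.** The rater's log is named in instructions that appear to be addressed to raters at visits. That does not show that other staff lack a route.
- **That no such question exists anywhere.** The measurement procedures cited as 1.4.2, the session-content table and pain-session description cited in 1.3.7, the detailed consent procedure, the event forms and the quality-of-life items are not in the supplied text. The finding is that no such question is listed there.

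**Conclusion.** The concern holds in a limited form. Section 3.4 states a rule that keeps mild events out of the record, and the supplied text lists no scheduled, recorded question on falls, injury or activity-related pain for either arm. Followed as written, the plan would probably miss minor or transient events and would give no descriptive tolerability data on these harms gathered alike in both arms.

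A reader might infer that the trial's results are biased or that its safety oversight fails. Neither follows. No between-arm analysis of adverse events is planned, so no planned estimate is affected. Serious and function-limiting events have a route to the record, and lasting functional harm would show in the follow-up measures.

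The conclusion rests on the supplied text being a fair guide to what is scheduled, and on mild soreness or a minor fall being treated as clinically insignificant, which the wording allows but does not require. Priority: minor to moderate.

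**What to change.** 1. In 3.4, name falls, musculoskeletal injury and worsening of typical daily pain as targeted events exempt from the exclusion. State in advance how many points on the 0-10 screening rating count as worsening. Leave the rest of the exclusion in place.
2. Ask one fixed, scripted question (any fall, injury or worse pain since last asked) at contacts that already exist: treatment sessions in weeks 3, 5, 7, 9 and 11, and the control calls nearest those weeks, assuming calls are about weekly.
3. Have the answers recorded on a form hidden from blinded raters, by unblinded staff other than the coordinator who randomizes. Section 1.3.5 keeps that person out of data collection, and the text does not say whether the same person makes the control calls.
4. Asker and mode differ by arm during treatment, so rest the between-arm description mainly on two items: one w15 question with the same script, mode and staff role in both arms, worded to cover the whole period since baseline; and the typical daily pain rating, repeated by blinded raters at baseline and w15 and added to Table 1.
5. Report both descriptively by arm, with no test.

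Cost: 5 + 1 questions and 2 ratings make 8 items. At an assumed minute each, 8 × 30 = 240 min = 4 h in total for 30 participants, or 8 × 80 = 640 min = 10.7 h for 80. Add one form, one line in Table 1, and protocol and consent wording. These hours leave out the follow-up and classification of positive answers, which may be frequent because people with pain below 7/10 are eligible. There will be more non-serious events to log.
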